4.1 BRIEF SUMMARY

Aggressive behaviors inflict massive costs on the public health. Psychopathy — the tendency to be callous, manipulative, and lack remorse — is one of the most central predictors of aggression and a core feature of psychopathology. Psychopathic individuals' antisocial acts have long been thought to be due to an inability to empathize with their victims. However, recent work suggests that psychopathic individuals have intact empathic abilities. Instead of employing their empathy to help others, psychopathic individuals appear to use empathy to exact greater harm on their victims. Such *antisocial empathy*, its neural bases, and its effects on the aggression of psychopathic individuals remains unexamined. We propose a functional neuroimaging study in which we will recruit 36 healthy adult male participants, who are at the low and high extremes of the psychopathy distribution (18 per group). While undergoing functional MRI, participants will complete a psychological task that evokes antisocially- and prosocially-motivated empathic responding. We predict that psychopathic individuals will exhibit greater recruitment of the brain's cognitive empathy network when empathy facilitates antisocial goals (i.e., harming a competitor) and that this neural recruitment will predict greater aggression towards their targets. These findings will serve as an initial foray into this potential new frontier for research on psychopathy, empathy, and aggression. If supported, this novel approach would readily translate into new motivation-focused interventions and would inform biological and psychological models of the monumentally-costly phenomenon of psychopathic aggression.

4.2.a NARRATIVE STUDY DESCRIPTION

Aggressive behavior is a substantial public health concern in the United States, with approximately 1.2 million violent crimes occurring in 2015¹. Such violent crimes (e.g., aggravated assault, murder, rape) resulted in over 1.5 million non-fatal injuries and over 17,000 deaths in 2015². Psychopathy is a well-established risk factor for such violence. Understanding the psychological factors (such as antisocial empathy) that explain such psychopathic aggression), as well as the neural mechanisms that transmit these effects, is crucial to developing effective and targeted psychological and pharmacological interventions that seek to reduce such violent outcomes. This project will empirically investigate these phenomena.

4.2.b PRIMARY PURPOSE

Basic Science

4.2.c INTERVENTIONS

Behavioral

4.2.d STUDY PHASE

N/A

4.2.e INTERVENTION MODEL

Other: Within-participants, repeated-measures experimental manipulation (randomized order)

4.2.f MASKING

Participant - Yes

Care Provider - No

Investigator - Yes

Outcomes Assessor - No

4.2.g ALLOCATION

N/A

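### The outcomes assessor is listed as unmasked without naming the factor; psychopathy group should be withheld until fMRI quality control, exclusions and signal extraction are locked

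*Combined protocol and SAP*

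**What the plan says.** Section 4.2.f gives four masking entries and nothing else: "Participant - Yes", "Care Provider - No", "Investigator - Yes" and "Outcomes Assessor - No". No entry names the factor concerned, and none is explained.

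The design has two factors (section 4.4). Empathy type is manipulated within each person; section 4.2.e describes the model as "Within-participants, repeated-measures experimental manipulation (randomized order)". Psychopathy is not allocated: section 4.1 recruits men "who are at the low and high extremes of the psychopathy distribution (18 per group)", and section 4.2.g gives allocation as not applicable. Section 4.1 also states a direction, namely that psychopathic individuals will recruit the cognitive empathy network more strongly when empathy serves an antisocial goal. Section 4.4 bases power on the interaction of the two factors.

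The two primary outcomes in section 4.3 are the accuracy of participants' pain ratings and the BOLD signal change in the cognitive empathy network, each comparing antisocial with prosocial trials. The document does not say who processes the images, how scans or runs are excluded, or how the network signal is extracted.

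**The concern.** BOLD signal is recorded by a machine, but the value that enters the analysis is not purely mechanical. Someone decides which scans fail for motion, which runs are dropped and how signal is drawn from the network. With 18 people per group, a handful of such decisions can matter. With no written rules, masking is the main remaining safeguard, and the one entry that would normally cover this work says it is absent.

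Randomising trial order does not help here. It protects the comparison of conditions within a person from order effects. It gives no protection against decisions made differently for high- and low-psychopathy participants, and a larger sample would not by itself cure a systematic tilt. What is at stake is the fMRI interaction: decisions that lean towards the predicted direction would produce apparent support for the hypothesis.

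The participant entry also invites a question. The antisocial condition is described as operating "when empathy facilitates antisocial goals (i.e., harming a competitor)", which suggests that participants know the goal of a trial. If so, the participant entry cannot refer to condition.

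**Working it through.** The document gives no figure to reproduce for this point. The check has two parts.

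**1. What the entries can mean**

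- *Outcomes assessor, not masked.* The factor could be group, condition or both. Condition has to be known at some stage in order to form the antisocial-minus-prosocial contrast. Group need not be known until the groups are compared. Group is therefore the factor for which masking is practicable and useful.
- *Investigator, masked.* This might cover the person who makes the analysis decisions. The document does not say.
- *Participant, masked.* According to section 4.1, "participants will complete a psychological task that evokes antisocially- and prosocially-motivated empathic responding". A manipulation that works through the participant's goal fits masking to the hypothesis or to group status. It does not fit masking to condition.

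**2. How large a tilt could be**

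Inputs from the document: 18 per group, and a directional hypothesis. Assumptions:

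- no true effect;
- each participant's antisocial-minus-prosocial contrast is normal with SD 1, so the interaction is a two-sample comparison of contrasts;
- two-sided 5% test, counting only rejections in the predicted direction (nominally 2.5%);
- k borderline scans per group, each kept only if its own contrast value favours the hypothesis.

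Under the null each borderline scan is favourable with probability 1/2, and a favourable one lies on average √(2/π) = 0.798 SD from zero. If B, binomial(k, 1/2), of them are kept, the expected difference between groups is

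shift = 2 × 0.798 × E[B / (18 − k + B)].

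- k = 2: E = (2/4)(1/17) + (1/4)(2/18) = 0.0572; shift = 0.09 SD.
- k = 3: E = (3/8)(1/16) + (3/8)(2/17) + (1/8)(3/18) = 0.0884; shift = 0.14 SD.
- k = 4: E = (4/16)(1/15) + (6/16)(2/16) + (4/16)(3/17) + (1/16)(4/18) = 0.1215; shift = 0.19 SD.

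On average 18 − k/2 scans per group remain, so SE ≈ √(2/(18 − k/2)). The directional rejection rate is about 1 − Φ(1.96 − shift/SE):

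- k = 2: SE 0.343, ratio 0.27, rate 4.5%.
- k = 3: SE 0.348, ratio 0.41, rate 6.0%.
- k = 4: SE 0.354, ratio 0.55, rate 7.9%.

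Simulation with 20,000 null datasets per setting agrees, apart from simulation error:

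| Borderline scans per group | Shift (SD) | Directional false positives |
|---|---|---|
| 0 | 0 | about 2.5% |
| 2 | 0.09 | 4.1 to 4.5% |
| 3 | 0.14 to 0.15 | 5.9 to 6.0% |
| 4 | 0.19 to 0.20 | 7.5 to 8.0% |

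**The same calls without sight of the outcome.** If the analyst knows the group but decides without seeing the contrast value, a kept scan has expected value zero whichever group it belongs to. The expected shift is zero. In simulation there was no shift and the rate stayed at about 2.5%. The tilt in the table therefore needs both pieces of information, the group label and the contrast value.

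**The case against.** The strongest reply is that the document never says the person who cleans the data is unmasked to psychopathy group. The assessor might be whoever runs the scanning session, with images processed by someone else. The masked investigator might be the person who makes the analysis decisions, in which case the risk is already covered. This stands. A reader might infer from the assessor entry that group-aware processing is planned, but the text supports only that it is not excluded.

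Second, the figures describe outcome-driven exclusion with every call going one way, not unmasked quality control in general. If exclusions are settled before contrasts are computed, knowing the group produces no such shift. This also stands, and it limits the size. A fixed exclusion rule written in advance would be another remedy, but the document contains none.

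Third, neither primary outcome is described as rater-judged. Rating accuracy may be scored automatically, so masking may add little there. This stands, and the concern is confined to the fMRI outcome.

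Fourth, a reader might infer that the participant entry is false because participants must know the condition. The document does not support calling it an error. The entry names no factor, the task procedure is not described, and the entry would be correct for the hypothesis or for group status. What is missing is the statement of which is meant.

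**Conclusion.** The point holds as a cheap protection worth adding to a stated choice, not as a demonstrated bias. The assessor is listed as unmasked, with no factor and no reason given, in a study whose key contrast is directional, compares selected groups and involves fMRI processing for which no rules are written.

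The size, about 0.14 to 0.20 SD and 6 to 8% directional false positives against 2.5%, is an upper illustration. It rests on an assumed 3 to 4 borderline scans per group, on every call favouring the hypothesis, and on calls made with both group and contrast value in view. With 2 such scans it is 0.09 SD and 4.1 to 4.5%; with calls made without the outcome it is nil. These figures should not be read as an estimate of this study's error rate.

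The participant and investigator entries need a clarifying sentence and nothing more.

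**What to change.** 1. In section 4.2.f, change the outcomes-assessor entry to masked, and state that the masking is to psychopathy group.
2. Code the imaging files with neutral IDs that do not reveal group. Complete and lock fMRI preprocessing, quality control, exclusions and network-signal extraction before the psychopathy label is merged.
3. As a clarification, say what the participant and investigator entries refer to. For participants this is presumably the hypothesis or group status rather than condition. For the investigator, say whether the entry covers the person who makes the analysis decisions.

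The cost is recoding file names, holding back one variable until the lock, and a sentence or two of text. No participants, scans or visits are added. The document does not describe staffing or workflow, so that the cost is minor is a judgement, though a reasonable one for data processed after the session. Withholding the group label protects the interaction; completing exclusions before contrast values are inspected would also protect the antisocial-versus-prosocial comparison itself.

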4.3 OUTCOME MEASURES

Primary - Change in accuracy of empathic pain judgments

Time frame: collected during intervention.

Brief description: Accuracy rates for pain ratings of faces during antisocial empathy trials (as compared to prosocial empathy trials).

NIH-Defined Phase III Clinical Trials: N/A

Primary - Change in brain activity assessed by fMRI

Time frame: collected during intervention.

Brief description: Blood-Oxygen-Level-Dependent signal change (as assessed by functional MRI) in the cognitive empathy brain network during antisocial empathy trials (as compared to prosocial empathy trials).

NIH-Defined Phase III Clinical Trials: N/A

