4.4 STATISTICAL POWER AND DESIGN

The MRI Study will employ a 2 (psychopathy: high vs. low) x 2 (empathy-type: antisocial vs. prosocial) mixed-effects design. The outcome variables are pain ratings and brain activity during such pain ratings. G*Power statistical software (version 3.1) was used to conduct power analyses for this interactive effect, revealing that such a moderation model will have at least 80% power to detect a modest interactive effect size estimate of $f = .08$ with 36 participants, 18 per group.

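### Do two primary outcomes with no stated alpha or success rule leave the plan's single 80% power figure in need of correction?

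*Combined protocol and SAP*

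**What the plan says.** Section 4.3 labels two outcomes primary: "Primary - Change in accuracy of empathic pain judgments" and "Primary - Change in brain activity assessed by fMRI". The first is described as "Accuracy rates for pain ratings of faces during antisocial empathy trials (as compared to prosocial empathy trials"; the second is the BOLD signal change in the cognitive empathy network over the same two trial types. Neither entry mentions psychopathy group.

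Section 4.4 sets out a "2 (psychopathy: high vs. low) x 2 (empathy-type: antisocial vs. prosocial) mixed-effects design" and adds: "The outcome variables are pain ratings and brain activity during such pain ratings". The power statement, made for the interaction, is that "such a moderation model will have at least 80% power to detect" an effect of f = .08; the sample is 36, split evenly into two groups of 18.

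Section 4.1 predicts that psychopathic participants will recruit the cognitive empathy network more when empathy serves an antisocial goal, and that this recruitment will predict aggression. It describes the work in these terms: "These findings will serve as an initial foray into this potential new frontier". Section 4.2.b gives the purpose as basic science.

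No section states alpha, sidedness, an order of testing, an adjustment for two outcomes, or a rule for combining them.

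**The concern.** With two primary outcomes, the power of one test is not the chance that the study succeeds, and a 5% level per test is not a 5% level for the pair. Without a success rule a reader cannot tell which chance the single figure describes. Nor does the plan say how to read a mixed result, with one outcome significant and the other not. If the rule were in effect that either will do, the false-positive chance could approach twice the nominal level.

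The wording also differs between sections. Section 4.3 contrasts trial types without mentioning group, while section 4.4 powers the group by trial-type interaction. Section 4.3 speaks of accuracy, section 4.4 of pain ratings. At first reading the primary test itself seems to need inferring.

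**Working it through.** **Inputs from the plan:** two primary outcomes (4.3); power at least 80%, f = .08, N = 36, 18 per group, two trial types (4.4). **Assumed, because not stated:** two-sided .05, one test per outcome, correlation r between the two test statistics from 0 to .9, and correlation ρ between a participant's two repeated measures.

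**1. The plan's own figure.** Under the usual G*Power convention for a within-between interaction, the noncentrality is λ = f² × N × m / (1 − ρ) with m = 2, on 1 and 34 degrees of freedom. Here f² × N × m = .0064 × 36 × 2 = .4608.

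| ρ | λ | power at .05 |
|---|---|---|
| 0 | .461 | 10% |
| .5 | .922 | 15% |
| .8 | 2.304 | 31% |
| .9 | 4.608 | 55% |

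Power of 80% needs λ = 8.317, so ρ = 1 − .4608/8.317 = .945. The plan does not give ρ, so the 80% is neither confirmed nor refuted here. It is a premise for step 3 only.

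**2. False positives.** These do not depend on the 80%.

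- Either suffices, unadjusted, independent tests: 1 − .95² = .0975. From the bivariate normal: .0907 at r = .5, .0835 at r = .7, .0704 at r = .9.
- Both required: both can be significant only if each true null is rejected, so the chance is at most .05. With both nulls true and independent tests it is .05² = .0025.

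**3. Chance of success if both effects are real and each test has 80%.** P(either) = 1.60 − P(both).

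| r | both | either, unadjusted | at least one, Holm |
|---|---|---|---|
| 0 | .8² = 64% | 1 − .2² = 96% | 91% |
| .5 | 69% | 91% | 85% |
| .7 | 71% | 89% | 82% |
| .9 | 75% | 85% | 77% |

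At r = 1 the first two columns meet at 80%. Holm also costs power for a single outcome: if only one effect is real, its power drops from 80% to about 70%.

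**4. How firm step 3 is.** Replace 80% by the 15.4% that f = .08 gives at ρ = .5, with independent tests. Then both succeed with chance .154² = 2%, and at least one with chance 1 − .846² = 28%. The success ranges therefore describe this study only if ρ is near .945.

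**5. Which test is primary.** Section 4.4 names the 2 × 2 design, calls the model a moderation model, and attaches the power to the interaction. The prediction in 4.1 is likewise a group difference in the antisocial condition. Section 4.3 defines what is measured, which need not repeat the group comparison. Its description of accuracy is of accuracy rates for pain ratings, so the shorter label in 4.4 reads as shorthand for the same task. An effect size expressed as f for this design points to a non-directional F test with one numerator degree of freedom.

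**The case for a change.** The best argument for a change is that it would be cheap: one or two sentences stating alpha and the success rule, with no extra participants or data. Exploratory status lowers the stakes but does not settle how a mixed result should be read. Section 4.7 commits the study to public reporting, and a rule fixed beforehand removes the temptation to pick one afterwards.

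Part of this stands. The alpha and the rule are indeed absent, and writing them down would be good practice. The 9.75% is also not a ceiling if the BOLD outcome is tested in several regions, since the plan does not give the number of tests in the network.

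The argument does not show that anything in the plan is wrong. The plan nowhere claims success on either outcome, so the inflated error rate belongs to a rule it has not adopted. The 80% is presented as the power of one interaction model, and nothing in section 4.4 offers it as the chance of overall success. The choice of rule is a real trade-off: requiring both lowers the chance of success to 64–75% on the 80% premise, while Holm takes about ten points from an outcome whose effect is the only real one. Treating a behavioural and a neural outcome as two separate questions, each at .05, is also defensible here. Adding the success ranges to the plan would do harm, because they rest on an unverified 80%.

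**Conclusion.** No change is called for. The gap is one of detail that analysts would fill sensibly: test the interaction for each of the two outcomes at two-sided .05 and report both. A Bonferroni or Holm correction for two tests needs only the two p values, so a reader who wants family-wise control can apply it to the published results. A mixed result can be read against section 4.1, whose explicit prediction concerns neural recruitment.

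The most at stake is a false-positive chance of 7.0–9.75% instead of 5%, and only if either outcome is taken as sufficient, without adjustment, at an assumed two-sided .05 with one test per outcome and r between .9 and 0. If both are required it is at most 5%. The difference between accuracy and pain ratings is a matter of labelling, and the interaction is identifiable as the powered test.

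This conclusion covers the missing success rule only. It does not endorse the 80% itself, which under the convention used above needs an unstated repeated-measures correlation of about .945.

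### Does the accuracy primary outcome in 4.3 need a stated scoring rule and reference value before the plan can stand?

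*Combined protocol and SAP*

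**What the plan says.** Section 4.3 lists two primary outcomes. The behavioural one is headed "Primary - Change in accuracy of empathic pain judgments", with the description "Accuracy rates for pain ratings of faces during antisocial empathy trials (as compared to prosocial empathy trials" and the timing "Time frame: collected during intervention". Nothing further is said about how a rating is scored.

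Section 4.1 describes the task in one clause: "participants will complete a psychological task that evokes antisocially- and prosocially-motivated empathic responding". Section 4.4 sets out a "2 (psychopathy: high vs. low) x 2 (empathy-type: antisocial vs. prosocial) mixed-effects design" and says "The outcome variables are pain ratings and brain activity during such pain ratings". It does not repeat the word accuracy. Sections 4.5 to 4.7 do not bear on scoring.

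**The concern.** An accuracy rate needs two things that a raw rating does not: a value against which each face is scored, and a rule that turns the distance from that value into right or wrong. Neither is in the document, so two analysts who both follow 4.3 could compute different primary results from the same ratings, and the choice could be made after the data are seen.

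The rationale sharpens the point. Section 4.1 argues that "recent work suggests that psychopathic individuals have intact empathic abilities" and that the difference lies in how empathy is used. It then matters whether the score measures how well pain is read, or also moves when one group simply rates everything higher or lower. At stake is the meaning of one of only two primary outcomes, and the ease with which it detects a difference. The fMRI primary is not affected.

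**Working it through.** **1. Is the definition elsewhere?** Reading 4.1 to 4.7 for a scale, a reference, a tolerance or a per-participant summary finds none. The phrase in 4.4 is most naturally shorthand for the 4.3 outcome. It neither competes with that outcome nor completes it.

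**2. Does any stated figure depend on the definition?** The only statistical figure is in 4.4: at least 80% power for an interaction of f = .08 with 36 participants, 18 per group. It is in standardised units and uses no scoring rule, so it does not change. Whether that figure is itself right is a separate question.

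**3. Can the reference matter?** The documents give no scale, noise or bias, so everything in steps 3 to 5 is assumed. Let noise have SD 1, let b be the rating shift relative to the reference, and let k be the tolerance. Then accuracy is A(b, k) = Φ(k − b) − Φ(−k − b). Suppose the high-psychopathy group rates antisocial trials 0.5 SD higher and nothing else differs.

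| k | A(0, k) | A(0.5, k) | Group × empathy-type difference, fixed reference |
|---|---|---|---|
| 0.5 | 38.29% | 34.13% | −4.2 points |
| 1 | 68.27% | 62.47% | −5.8 points |
| 1.5 | 86.64% | 81.86% | −4.8 points |

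If each face is instead scored against the sample's own mean rating in that condition, the reference moves by 0.5 × 18/36 = 0.25. The groups then sit at +0.25 and −0.25. A is symmetric in b, so they are equally accurate and the difference is 0.0 at every k.

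**4. Can the rule matter?** Take rating = reference + bias + normal noise, rounded and clipped to a 1-7 scale, with references spread evenly over the scale points. The high group's noise SD falls from 1 to 0.8 in antisocial trials. Entries are accuracy at SD 1 and the change in percentage points.

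| Bias (points) | Exact match | Within 1 point |
|---|---|---|
| 0 | 47.1%, +7.3 | 90.5%, +5.2 |
| −0.5 | 43.5%, +4.5 | 87.0%, +5.0 |
| −1 | 35.0%, −0.5 | 77.5%, +3.4 |
| −1.5 | 25.9%, −3.1 | 64.2%, +0.1 |

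A 0-10 scale gives the same pattern (+7.7 and +6.0 when unbiased; −0.6 and +3.9 at −1). So the choice can matter, and signs can differ.

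**5. Do the documents point to a better rule?** The candidate is a fixed reference with a 1-point tolerance. Power was simulated with 18 per group, two-sided 0.05, 42 faces per condition, person bias SD 0.5 and person-by-condition bias SD 0.25. Exact match against within-1 gives 22% v 38% (unbiased), 14% v 26% (0.5 low) and 4% v 9% (1 low). That favours within-1, but the advantage does not survive modest changes:

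- **Sign.** With the bias taken past −1.5 on the 1-7 scale, within-1 gives −1.7 at −1.75 and −3.0 at −2. It reverses too, only later than exact match.
- **Power.** With noise SD 0.5 and bias SDs halved to 0.25 and 0.125 (unbiased, 42 faces), within-1 starts from 99.8% accuracy. It has 0.2 points to gain, against 9.1 for exact match. Simulated power is about 13%, against 37 to 39% for exact match.
- **Shift.** Step 3 shows that any fixed reference responds to a pure rating shift. The 1-point tolerance at noise SD 1 is the most responsive of the three shown (−5.8). Prescribing it would leave the interpretive worry where it was.

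**The case for a change.** The best case for a change is that the scoring rule is open on a primary outcome, that steps 3 and 4 show reasonable choices giving different sizes and sometimes opposite signs, and that writing the rule down takes a few sentences and alters neither task nor sample. An open rule also leaves room to choose after seeing the results. If a task manual already holds the rule, copying it across is trivial.

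Much of this stands. The definition is absent from this document, and recording the task's own scoring before analysis is good practice.

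What does not stand is the step from there to a fault in the plan. A request to write down whatever rule the task already has asks for detail; it corrects nothing. The document is a short record with a few lines per field, so its silence does not show that the study lacks a rule. The illustrations show that a difference is possible, not that it is likely. The 0.0 in step 3 follows from choosing a sample-mean reference with equal groups, which nothing in the documents suggests, and the sign conflict in step 4 needs raters a full point low on average. Finally, the prediction written in 4.1 concerns neural recruitment and aggression, not rating accuracy.

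**Conclusion.** No change to the plan is called for. The observation is correct: 4.3 names an accuracy rate without a scale, a reference or a rule. But this is a gap that analysts would ordinarily fill from the task's own scoring and state when they report. No passage contradicts another, and no stated figure moves.

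The possible effect is a few percentage points in the antisocial-minus-prosocial contrast: 0.0 v −5.8 for the choice of reference at a tolerance of 1 SD, and +7.3 v +5.2 for the choice of rule with unbiased raters. All of it rests on assumed scale, noise, bias and number of faces. The choice between rules is a trade-off. Exact match loses sensitivity and changes sign earlier when raters are biased; a tolerance band meets a ceiling when ratings are precise; and any fixed reference responds to overall shifts. Without the scale or the noise, the documents cannot show that one rule is better.

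The judgement would differ if the document stated a scoring rule that conflicted with 4.3, or if a stated figure had been derived from one. Neither is the case.
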